#### 6.3.5 Clinical Assessments, Including TB Evaluations

##### Complete Physical Exam

A complete physical examination will be performed at screening only and will include at a minimum an examination of the skin, head, mouth, and neck; auscultation of the chest; cardiac exam; abdominal exam; examination of the lower extremities for edema; and Karnofsky performance score. The complete physical exam will also include signs and symptoms, diagnoses, vital signs (temperature, pulse, respiration rate, and blood pressure), and a measurement of height and weight. Standardized blood pressure is not required for A5290.

##### Targeted Physical Exam

After screening, a targeted physical examination is to be driven by any previously identified or new signs or symptoms including diagnoses that the participant has experienced since the last visit. This examination will include weight, vital signs

(temperature, pulse, respiration rate, and blood pressure), examination for the presence of thrush, lymphadenopathy, presence of rash, and lung examination.

#### Signs and Symptoms

At entry, all grades that occurred within 30 days prior to study entry must be recorded; post-entry, all signs and symptoms  $\geq$  Grade 3 must be recorded. Record all signs and symptoms that led to a change in treatment, regardless of grade.

At entry, all TB-related signs and/or symptoms that occurred within 30 days prior to study entry must be recorded. These include, but are not limited to, fever, weight loss, lymphadenopathy, pulmonary signs and symptoms, and evidence of extrapulmonary disease (e.g., meningitis), presence of wasting, cold abscesses, or abdominal disease.

After entry, resolution of TB-related signs and symptoms reported at entry will be recorded. Any new or resolved Grade  $\geq$  2 TB signs or symptoms reported after entry will be recorded on the CRF.

#### TB Evaluations

A review of all reported results from evaluations for the qualifying episode of TB performed at the local clinical or TB program site must be completed for all participants. At each visit, all diagnostic, laboratory and radiology results, and treatment information available regarding the qualifying (current) episode of TB, including any that is provided by the local TB clinic, must be recorded on the CRFs when received. This will include TB-related radiologic results, including most recent chest x-ray, AFB smear and culture results, and other evaluations related to TB diagnosis and evaluation of TB status. Any changes in results from repeated radiologic evaluations must be documented.

Participants whose qualifying episode of TB is later identified as drug-resistant according to the inclusion and exclusion criteria in section 4.0 will be discontinued from the study and referred to their primary clinician/clinical facility or TB and ART program and treated with the best available TB and ART according to local standards of care. Sites must notify the A5290 core team by e-mail ([[contact]](mailto:[contact])) within 2 weeks after learning that the participant's TB has been identified as drug-resistant.

Participants whose qualifying episode of TB was later deemed to be not TB will continue to be followed on study, off study-provided TB treatment, but on study-provided ART, for safety and ART endpoints.

Cultures from study samples identified as TB-positive, including any sample that is positive for drug-resistance, must be stored at the site laboratory or the local TB laboratory performing the TB testing (as appropriate to site procedures).

**Diagnoses**

Diagnoses identified by the ACTG criteria for clinical events and other diseases received since the last visit must be recorded. Refer to the study CRF for the appropriate appendix used for the current ACTG criteria.

**Concomitant Medications**

After entry, all concomitant prescription medications, excluding TB medications, started or stopped since the last visit must be recorded on the CRF. Nonprescription medications will be recorded in the source documents only. Non-study provided TB medications will be recorded on the TB Treatment CRF and all non-study provided ART will be recorded on the ARV Treatment CRF.

**HIV and TB Study Treatment Modifications**

Record all ARV and anti-TB study drug modifications, including initial doses, modifications that were participant-initiated and/or protocol-mandated and/or according to local/national/international guidelines, and inadvertent and deliberate interruptions of ARVs for > 3 days and anti-TB medications for > 7 days at each visit. Record any permanent discontinuation of any ARV or anti-TB drug.

**6.3.6 Adherence Assessment - Pill Counts**

Pill counts for all prescribed ARVs and TB medications will be conducted according to the SOE.

**6.3.7 TB Treatment Status and Outcome Determination**

At completion of the entire course of TB treatment, TB treatment status/outcome must be recorded on the CRF, and should also be documented again at weeks 48 and 72, at the time of detection/diagnosis of TB treatment failure or TB relapse/recurrence or at the time of premature discontinuation or death.

TB treatment status/outcome will be classified according to the following, adapted from ATS guidelines.

**Cure:** Completion of all recommended doses of medication *and* 2 consecutive TB-negative mycobacterial cultures.

**Treatment failure:** TB-positive mycobacterial culture after 16 weeks of TB treatment for a participant who was documented to be taking TB medications.

**Died:** Participant who died for any reason before the completion of TB-treatment.

**Default:** Participant whose TB-treatment was interrupted for 2 or more consecutive months and did not reinitiate TB therapy.

**Transfer out/lost to follow-up (LTFU):** Participant who was transferred to another treatment facility or LTFU and for whom the TB treatment outcome is not known.

**Treatment ongoing:** At time of evaluation, participant is still undergoing treatment for TB. Documentation should be made of why prolonged TB treatment is occurring, including: default with reinitiation of TB treatment, initial TB treatment failure, and persistent TB-positive mycobacterial cultures.

**Relapse/recurrence:** Participant who has 2 consecutive TB-negative mycobacterial cultures and who subsequently has clinical or radiographic deterioration consistent with active TB at or after week 24 and before the week 72 endpoint.

**Treatment completed:** Participant who has completed TB treatment but who does not meet the criteria to be classified as a cure or a failure.

**NOTE:** For participants who are enrolled with probable TB and do not have a positive mycobacterial culture from any site available to meet these outcome definitions, but who have specimens with a positive AFB smear, the AFB smear result will be substituted for the mycobacterial culture result in assessing TB outcomes. If there are no positive AFB smear results, then the assessment of TB outcomes will be based on best clinical judgment and further reviewed by the team and an independent endpoint reviewer.

#### 6.3.8 Chest X-Ray

A chest X-ray must be performed within 30 days prior to study entry, at weeks 8, 48, and 72, at the time of suspected TB treatment failure or relapse/recurrence, and at premature study discontinuation. Interpretation of the x-ray is to be performed by a clinician.

#### 6.3.9 Laboratory Evaluations

At screening and entry all protocol required laboratory values must be recorded on the CRFs. For post-entry assessments, record all Grade  $\geq 3$  laboratory values. All laboratory toxicities that led to a change in treatment, regardless of grade, must be recorded.

##### Hematology

Hemoglobin, hematocrit, red blood cells, mean corpuscular volume, white blood cell count (WBC), differential WBC, ANC, and platelets.

##### Liver Function Tests

Total bilirubin, AST (SGOT), ALT (SGPT), and alkaline phosphatase.

##### Blood Chemistries

Sodium, potassium, chloride, bicarbonate, creatinine, and albumin.

**Pregnancy Test**

For women with reproductive potential: Serum or urine  $\beta$ -HCG (urine test must have a sensitivity of 15-25 mIU/mL).

**CD4+/CD8+**

Obtain absolute CD4+/CD8+ count and percentages within 30 days prior to study entry from a laboratory that is certified for protocol testing by the DAIDS Immunology Quality Assurance (IQA) Program. For entry and post-entry evaluations, the laboratory must be certified by the DAIDS Immunology Quality Assurance (IQA) Program.

#### 6.3.10 Virologic Studies

**Plasma HIV-1 RNA**

Screening HIV-1 RNA must be performed within 30 days prior to study entry by a laboratory that possesses a CLIA certification or equivalent. For entry and post-entry evaluations, the laboratory must be certified by the DAIDS Virology Quality Assurance (VQA) Program.

**HIV Resistance Testing (Stored Plasma)**

HIV resistance testing will be performed retrospectively (not in real time), using a VQA certified method. Refer to the A5290 Laboratory Processing Chart (LPC) for additional details.

**Stored Plasma and PBMC**

Plasma will be stored for future virology testing as indicated in the SOE. Refer to the A5290 LPC for details of collection, processing, shipping, and designated laboratory. At sites that are able to, PBMCs (viable, whenever possible) will be cryopreserved for future virology and immunology testing.

#### 6.3.11 Pharmacokinetic Studies

See section 10.0, Pharmacology Plan.

Participants do not have to be fasting when they come to the clinic for their PK study. Site staff should advise the participant that if he/she does eat prior to coming to the clinic to avoid high fat meals. If the sites provide a meal on the PK day, it should not be a high fat meal and it should be provided 3 hours after the dose of LPV/RTV and either RBT or RIF has been given. Any kind of a snack or meal can be provided after that 3 hour post dose meal. (See section 5.1.3.)

Participants' PK samples collected during the dose-finding period in accrual period 1 will be batched and shipped to the ACTG repository every 2 weeks with immediate re-shipping to the PK laboratory. Otherwise, PK samples will be batched and shipped to the ACTG repository periodically. Refer to the A5290 LPC for additional instructions.

### 6.3.12 Stored Serum

Serum samples will be collected as per the SOE and stored for future immunology testing. Refer to the A5290 LPC.

### 6.3.13 Stored Urine

Urine will be stored for future TB biomarker testing as per the SOE. Refer to the A5290 LPC.

### 6.3.14 Sputum Sample Storage

Samples will be collected as per the SOE and stored as per the A5290 LPC.

## 7.0 CLINICAL MANAGEMENT ISSUES

A5290 will use the Division of AIDS Table for Grading the Severity of Adult and Pediatric Adverse Events Version 1.0, December 2004, Clarification August 2009, as a guideline for grading toxicities.

Toxicity management at non-US sites may require reliance on clinical symptoms, clinician judgment, and available laboratory markers, since alternatives to study-provided ARV drugs may be very limited and baseline levels of certain laboratory parameters (e.g., hemoglobin) may be different than in other settings.

This section provides guidelines for management of pregnancy and breastfeeding and of toxicities related to study-provided drugs LPV/r, RBT, and RAL only. When one of the ARV drugs is held for resolution of toxicity, all drugs in the ARV regimen should be held concurrently. With the exception of RBT, toxicity management of the TB medications will be performed by local TB control programs or the site investigator according to local standards in close communication with the A5290 protocol team.

Every attempt should be made to continue to follow participants who discontinue ARVs and/or TB drugs because of a Grade 3 or 4 AE until resolution of the adverse event can be documented.

The A5290 Clinical Management Committee (A5290 CMC) is available to discuss toxicity management of study-provided and other ARVs and TB drugs with investigators. The A5290 CMC consists of the A5290 protocol chairs, statisticians, DAIDS medical officer, DAIDS pharmacist, data managers, clinical trials specialist, and other protocol team members selected by the A5290 protocol chairs.

## 7.1 Toxicity Management

### Grade 1 or 2

Participants who develop a Grade 1 or 2 AE or toxicity may continue ARVs and TB drugs without alteration of the dosage. Participants experiencing Grade 1 or 2 toxicities will be managed at the discretion of the site investigator.

### Grade 3

If there is compelling evidence that the AE has NOT been caused by the study-provided drugs, dosing may continue at the discretion of the site investigator/clinician. Except as stated in the following sections, participants who develop a Grade 3 AE or toxicity thought to be secondary to study-provided drugs or of unknown etiology may have all of their ARVs and/or TB drugs withheld, at the site investigator's discretion. Investigators are welcome to discuss toxicity management with the A5290 CMC. The participant should be reevaluated weekly if at all possible until the AE returns to Grade  $\leq 2$  or until stabilized and no longer in need of such frequent monitoring, as determined by the site investigator, at which time ART and/or anti-TB treatment may be reintroduced at the discretion of the site investigator or according to standard practice.

### Grade 4

Participants who develop a symptomatic Grade 4 AE or toxicity, not specifically addressed below, will have all medications withheld and should be reevaluated weekly if at all possible until the AE returns to Grade  $\leq 2$  or until stabilized and no longer in need of such frequent monitoring, as determined by the site investigator. However, under certain circumstances the ARV or TB drug thought most likely to be related to the AE may be resumed at the discretion of the site investigator. However, if study-provided ARV or TB drugs are permanently discontinued due to a toxicity not otherwise specified in section 7.2, then the participant should continue to be followed on study, off-study-provided medications and referred to their primary clinician for best available management.

Participants with Grade 4 asymptomatic laboratory abnormalities, not specifically addressed below, may continue ART and anti-TB treatment if the site investigator has compelling evidence that the toxicity is NOT related to the ART or anti-TB treatment, or if benefit of the ART or anti-TB treatment outweighs the potential risk.

## 7.2 Specific Management of Toxicities Related to Study-Provided Drugs

### 7.2.1 AST and ALT Elevation

ARVs, INH, RIF, RBT, and PZA can all cause alterations in liver function tests. Concomitant illnesses, including TB, may also alter these laboratory parameters. Therefore, changes in AST or ALT should be evaluated within the clinical context of the abnormalities.

Participants entering this trial will potentially have advanced HIV disease and active TB. Elevation in ALT and AST is expected. Because this study is designed to assess the risk/benefit ratio of second-line ART with varying doses of LPV/r

and RBT as an alternative for RIF in this population, participants with  $\leq 2 \times$  ULN for ALT will be allowed to enroll in accrual period 1 and participants with  $\leq 5 \times$  ULN for both parameters will be allowed to enroll in accrual period 2 of the study. If the AST or ALT elevation is considered most likely to be due to concomitant illness or medication, standard management, including discontinuation of the likely causative agent, should be undertaken.

For asymptomatic or symptomatic elevation of AST or ALT  $> 7.5 \times$  ULN (Grade 3), all medications should be discontinued and held until levels and symptoms are Grade  $\leq 2$ , at which time therapy may be reintroduced. All medications may be restarted if the laboratory abnormalities were thought secondary to a concomitant illness.

If the elevation of AST or ALT is thought to be due to RBT, anti-TB medications should be reintroduced one at a time in 3-7 day increments, and if all other anti-TB medications are tolerated, RBT should be added last, initially at a reduced dose according to Table 5.1. If the participant was already receiving RBT at a reduced-dose then the re-challenge dose should be the dose the participant was previously receiving. If the RBT dose is tolerated upon re-challenge for 7 days, then the ARVs should be restarted. If Grade 3 or higher elevation of AST or ALT recurs with the reintroduction of RBT then RBT should be permanently discontinued and the participant should be referred to his/her primary clinician or local TB program, provided the best available anti-TB therapy according to local standards, and the participant should continue to be followed on study but off study-provided anti-TB medications.

If the elevation of AST or ALT is thought to be due to LPV/r, anti-TB medications should be reintroduced one at a time in 3-7 day increments as described above, and if all anti-TB medications are tolerated upon re-challenge, then LPV/r should be re-introduced at the reduced dose according to Table 5.1 together with the NRTIs. If the participant was already receiving a reduced dose of LPV/r, then the re-challenge dose of LPV/r should be the dose the participant was previously receiving. If the LPV/r dose is tolerated upon re-challenge for 7 days, then the previous dose the participant was receiving, if applicable, may be restarted after discussion with the A5290 CMC. If Grade 3 or higher elevation of AST or ALT recurs with the reintroduction of LPV/r then LPV/r should be permanently discontinued, the participant should be referred to his/her primary clinician or local TB program and provided the best available ART according to local standards, and the participant should continue to be followed on study but off study-provided anti-HIV medications.

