Based primarily on results from studies in healthy volunteers, standard dose reductions of RBT have been recommended when administered with PIs, but there is a critical need to validate those recommendations among participants with HIV-related TB. Notably, the reduced dose of RBT would likely be inadequate for TB treatment if the PI therapy was discontinued. Therefore, the approach of reduced dose RBT relies on adherence to a PI and there may be differences among PIs with regard to the impact on PK/PD. In one small study, 10 HIV-infected participants hospitalized in a TB treatment facility were started on RBT-based TB treatment at a dose of 300 mg TIW without LPV/r, had week 2 RBT concentrations obtained, then added a LPV/r-based ART regimen and reduced their RBT dose to 150 mg TIW, per current recommendations. The  $C_{max}$  obtained at week 4 to 5 was  $\leq 0.30 \mu\text{g}/\text{mL}$  for 9 of 10 participants while the partially active 25-O-desacetyl metabolite of RBT was increased, as was the  $AUC_{0-24}$  and  $AUC_{0-48}$ . Most unbound RBT  $C_{max}$  values were below the minimum inhibitory concentration (MIC) for drug-susceptible MTB and values for the plasma concentration-time curve were below those that had been associated with TB treatment failure or relapse (i.e., an  $AUC_{0-24} < 4.5 \mu\text{g}^*\text{h}/\text{mL}$ ) in a previously conducted TB Trials Consortium Study. Eight of the 10 participants in the study were men with a median weight of 74 kg and a median body mass index (BMI) of 23.1, a heavier population with a different gender proportion than participants likely to be enrolled from some resource-constrained settings. In another report, three participants experienced a relapse of TB with a RIF-resistant isolate after treatment with a RTV-boosted PI-based ART regimen coupled with a RBT-based TB regimen using a 150 mg TIW dose schedule. These studies raise some uncertainty about current dosing recommendations for RBT in the setting of PI-based therapy, although results from a recent PK study conducted in South Africa shed further light on this issue. In this study, the PK of RBT was evaluated in 16 HIV coinfected participants with active TB. These participants were initially treated with a RBT-based anti-TB regimen (using RBT in a dose of 300 mg daily) before starting ART that included standard doses of LPV/r 400/100 mg BID daily. Participants were established on their anti-TB therapy and were then randomized after starting LPV/r to receive RBT 150 mg daily x 4 weeks followed by 150 mg TIW or to the converse dosing strategy. Serial RBT and 25-O-desacetyl RBT concentrations were measured after each 4 week interval. The median  $AUC_{0-24}$ , and  $C_{max}$  on RBT 300 mg daily, 150 mg TIW, and 150 mg daily, respectively, were 3026 ng/mL.h and 297 ng/mL, 2307 ng/mL.h and 168 ng/mL, and 5010 ng/mL.h and 311 ng/mL. All doses were well tolerated with only one case of uveitis that occurred prior to starting LPV/r and one episode each of Grade 2 transaminitis and neutropenia reported. When coupled with standard doses of LPV/r, the dose of RBT that best approximated the 300 mg dose in the absence of LPV/r, and that achieved a  $C_{max}$  concentration of RBT within recommended target ranges for TB treatment of 300-900 ng/mL, was the RBT 150 mg daily dose. These data in aggregate suggest that in the context of PI-based therapy, the current recommended dose of RBT is insufficient. Finally, RBT is not available in fixed-dose combination formulations of TB medications that are commonly used in high-burden settings. Therefore, the use of RBT, rather than RIF, will be associated with higher pill burdens and will be more complex for patients and TB control programs.

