C	LPV 400 mg/RTV 100 mg tabs BID + two NRTIs + RAL 400 mg BID	INH 300 mg daily, RBT 300 mg daily, then 150 mg daily upon initiation of ART*, EMB (weight-based dose) daily, PZA (weight-based dose) daily, and pyridoxine 25 mg daily. EMB and PZA will be discontinued after 8 weeks of treatment; INH, RBT 150 mg daily (or the adjusted dose determined by PK), and pyridoxine will continue for a minimum total duration of 24 weeks. INH, RBT, and pyridoxine may continue beyond the 24 weeks to a maximum of 48 weeks at the discretion of the primary clinician; the protocol core team must be notified.	LPV/r + two NRTIs + RAL will continue at standard dosing through week 72	This regimen follows the same rationale as for Arm A but adds RAL in an attempt to enhance the antiviral activity of LPV/r when combined with RBT to evaluate whether this approach is associated with a better virologic response than the other two arms.

\*NOTE: In Arms A and C, RBT should be administered at a dose of 300 mg daily until the start of antiretroviral therapy at which time the dose should be reduced to the 150 mg daily dose. If LPV/r is stopped prematurely during TB treatment, the RBT dose should be increased to 300 mg daily and the team should be notified. All participants will receive TB treatment according to in-country TB guidelines for daily TB treatment and directly observed therapy (DOT), except that all study participants will receive daily TB treatment 7 days per week, i.e., participants will not use a 5 days per week schedule that may be recommended in some in-country TB programs.

Accrual will take place in two accrual periods. Accrual period 1 will enroll participants who will undergo an initial dose-finding period before continuing regular study follow-up through 72 weeks. Once review of the dose-finding data in accrual period 1 is completed, accrual period 2 will begin.

#### Accrual Period 1

Sixty participants will be randomized 1:1:1 (20 participants per arm) to one of three treatment arms as detailed above. Anti-TB therapy with study-provided RBT or non-study-provided RIF and non-study-provided INH, EMB, and PZA should be started within 72 hours of randomization. ART should be started as soon as possible after initiating anti-TB therapy, but may be delayed for up to 7-14 days after starting anti-TB therapy to allow participants sufficient time to assess tolerability of TB medications. Participants will then undergo a formal PK and safety evaluation to include:

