If, based on the SMC's determination, unacceptable PK or safety criteria are met within two treatment arms, then further enrollment into the study may be stopped, and the accrual period 1 participants will be managed according to best available local TB and antiretroviral treatment. These participants will be followed off study medication for the remainder of study follow-up (up to 72 weeks).

Table 5.1. LPV/r and RBT Dose Adjustment Table

	LPV/r Dose Adjustment	Rifabutin Dose Adjustment
Arm A	No dose adjustment	
RBT PK parameters low: Adjust RBT to RBT 300 mg orally three times weekly (TIW) or 300 mg orally once daily (see section 10.4).
 
RBT PK parameters high: Decrease RBT to RBT 150 mg orally TIW
 
NOTE: The RBT <math>C_{max}</math> will be used for the purpose of individual dose adjustment for low or high RBT concentrations. A low RBT concentration will be < 250 ng/mL. A high

		RBT $C_{max}$ will be greater than 900 ng/mL.
Arm B	
 
LPV <math>C_{min}</math> < 1 mg/L and <math>C_{max}</math> < 12 mg/L: add LPV 200 mg/RTV 50 mg (one additional fixed-dose combination tablet) twice daily
 
LPV <math>C_{min}</math> < 1 mg/L and <math>C_{max}</math> > 12 mg/L: add one additional RTV 100 mg tab tablet twice daily
 
 
NOTE: A LPV <math>C_{12}</math> (or trough) will be used to define whether an individual subject's LPV/r dose is too low.
	N/A
Arm C	No dose adjustment	
RBT PK parameters low: Adjust RBT to RBT 300 mg orally TIW or 300 mg orally once daily (see section 10.4).
 
RBT PK parameters high: Decrease RBT to RBT 150 mg orally TIW
 
NOTE: See Arm A for definition of RBT low and high concentrations.

Rifabutin Dose Adjustment:

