### 7.2.2 Bilirubin

Participants entering this trial will potentially have advanced HIV disease and active TB. Elevation in bilirubin is common in this situation; however, asymptomatic or symptomatic elevation of bilirubin may also occur with RBT, RIF, or LPV/r. Because this study is designed to assess the risk/benefit ratio of second-line ART with varying doses of LPV/r and RBT as an alternative for RIF

in this population, participants with  $\leq 2.5 \times$  ULN of bilirubin will be allowed to enroll in accrual period 1 and participants with  $\leq 5 \times$  ULN of bilirubin will be allowed to enroll in accrual period 2 of the study. If the bilirubin elevation is considered most likely to be due to concomitant illness or medication, standard management, including discontinuation of the likely causative agent, should be undertaken.

For new Grade 3 bilirubin, study medications can be continued if, in the opinion of the site investigator, the possible benefits of therapy outweigh the risks.

For asymptomatic or symptomatic new elevation of bilirubin  $> 5 \times$  ULN (Grade 4), all medications must be discontinued and held until levels are Grade  $\leq 2$ , at which time therapy may be reintroduced. All medications may be restarted if the laboratory abnormalities are thought to be secondary to a concomitant illness. If the elevation of bilirubin is thought to be due to RBT, anti-TB medications should be reintroduced one at a time in 3-7 day increments, and if all other anti-TB meds are tolerated, RBT should be added last, initially at a reduced dose according to Table 5.1. If the participant was already receiving RBT at a reduced dose then the re-challenge dose should be the dose the participant was previously receiving. If the RBT dose is tolerated upon re-challenge for 7 days, then the ARVs should be restarted. If Grade 4 elevation of bilirubin recurs with the reintroduction of RBT, then RBT should be permanently discontinued and the participant should be referred to his/her primary clinician or local TB program, provided the best available anti-TB therapy according to local standards, and the participant should continue to be followed on study but off study-provided anti-TB medications.

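### Sections 7.2.1 and 7.2.2 restart rifabutin below 300 mg daily while LPV/r is held, and the protocol does not say whether its 300 mg rule for stopped LPV/r covers such a hold

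*Protocol*

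**What the plan says.** Toxicity rules. For AST or ALT above 7.5 x ULN, Protocol 7.2.1 says "all medications should be discontinued and held until levels and symptoms are Grade" 2 or lower. For new bilirubin above 5 x ULN, 7.2.2 says "all medications must be discontinued and held until levels are Grade" 2 or lower. If RBT is the suspected cause, the other anti-TB drugs come back one at a time, and then "RBT should be added last, initially at a reduced dose according to Table 5.1". For someone whose dose had already been lowered, 7.2.1 adds: "If the participant was already receiving RBT at a reduced-dose then the re-challenge dose should be the dose the participant was previously receiving". On antiretrovirals it says: "If the RBT dose is tolerated upon re-challenge for 7 days, then the ARVs should be restarted". Section 7.2.2 has the same sequence.

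The table they point to. For Arms A and C, the only downward RBT step in Table 5.1 (section 5.1.1) is "Decrease RBT to RBT 150 mg orally TIW", listed for high RBT concentrations.

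The LPV/r rule. The note under Table 3.1 in section 3.0 says: "If LPV/r is stopped prematurely during TB treatment, the RBT dose should be increased to 300 mg daily and the team should be notified". The Schema and 5.1.1 carry the same rule. They apply it whenever in TB treatment LPV/r is prematurely discontinued, and make the 300 mg dose provisional until the team advises further. The notes in 3.0 and 5.1.1 also keep RBT at 300 mg daily until antiretroviral therapy starts, when it drops to 150 mg daily.

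The stated reason. The Background (2.1) says that "the reduced dose of RBT would likely be inadequate for TB treatment if the PI therapy was discontinued".

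If LPV/r is the suspected cause, 7.2.1 and 7.2.2 bring back all the anti-TB drugs, RBT among them, before LPV/r. No RBT dose is stated for that interval.

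**The concern.** The re-challenge sequence creates a period in which RBT is taken and LPV/r is not. For that state the protocol holds two instructions that differ in dose, and neither refers to the other. Section 7.2 has no sentence setting the LPV/r rule aside, and the LPV/r rule has no exception for toxicity re-challenge. A site following 7.2.1 to the letter and a site following 5.1.1 to the letter would prescribe different RBT doses to the same participant.

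What is at stake is participant safety and uniform conduct across sites in Arms A and C. The protocol ties the lower RBT dose to the presence of a protease inhibitor and says why. It should therefore say what happens when the inhibitor is temporarily absent.

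**Working it through.** The plan gives no figure to reproduce here. The check sets the instructions side by side and converts each to milligrams per week.

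| Situation | Source (Protocol) | RBT instruction | LPV/r status |
|---|---|---|---|
| RBT-attributed re-challenge | 7.2.1, 7.2.2 | Table 5.1 decrease, or the earlier dose if already reduced | Off until 7 tolerated days of RBT |
| LPV/r prematurely stopped | Schema, 3.0, 5.1.1 | 300 mg daily | Off |
| Before antiretrovirals start | 3.0, 5.1.1 | 300 mg daily | Not yet on |
| LPV/r-attributed re-challenge | 7.2.1, 7.2.2 | None stated | Off until anti-TB drugs are tolerated |

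**Step 1: is LPV/r off while RBT is on?** Yes. All drugs are stopped first, and antiretrovirals resume only after RBT has been tolerated for 7 days. The overlap of RBT on and LPV/r off is therefore at least 7 days.

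**Step 2: what is the restart dose?** The Table 5.1 decrease is 150 mg three times weekly. A second reading is possible because 3.0 and 5.1.1 describe 150 mg daily, the ordinary dose on antiretrovirals, as the dose to which RBT is reduced. A site could then class the participant as already reduced and return to 150 mg daily.

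**Step 3: weekly dose = dose x number of doses per week.**
- Table 5.1 decrease: 150 x 3 = 450 mg
- 150 mg daily: 150 x 7 = 1050 mg
- LPV/r-stopped rule: 300 x 7 = 2100 mg
- Ratios to the LPV/r-stopped rule: 450/2100 = 21%; 1050/2100 = 50%

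Both readings of the reduced dose fall below 300 mg daily, so the conflict does not depend on which one is meant.

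**Step 4: can this be turned into exposure?** No. The figures in 2.1 from the South African RBT study are median 24-hour AUCs of 3026 ng/mL.h on 300 mg daily without LPV/r, and of 2307 (150 mg three times weekly) and 5010 (150 mg daily) with LPV/r. The documents give no concentration for either 150 mg schedule without LPV/r. The ratios in step 3 are ratios of prescribed milligrams only.

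**Step 5: the LPV/r-attributed branch.** RBT returns while LPV/r is off, but no RBT dose is written there. The back-reference to the preceding branch can be read as covering only the 3-7 day spacing. With no competing dose stated, this is a gap and not a contradiction.

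**The case against.** The strongest reply is that a hold is not a discontinuation. The 300 mg rule is triggered by premature discontinuation or stopping of LPV/r, while 7.2.1 and 7.2.2 describe a supervised pause with planned reintroduction. The protocol separates the two elsewhere. The tolerability endpoints in 9.2.3.3 put permanent discontinuation and treatment holds in different categories, 8.1 lists grounds for permanent ARV discontinuation, and 7.0 speaks of ARVs held until toxicity resolves. On this view section 7.2 is the specific rule and takes precedence. This stands in part: a reader might infer that the protocol issues two proven opposite orders, and the documents do not go that far. What they leave open is scope. They do not settle it in favour of section 7.2 either: 7.2.1 and 7.2.2 use both verbs for the same act, the Schema and 5.1.1 set no limit on timing, 300 mg daily is also the dose before antiretrovirals start, and the Background's reason is the absence of the inhibitor.

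Second, the 300 mg dose is provisional in the Schema and 5.1.1, section 7.0 describes its content as guidelines, and the Clinical Management Committee can be consulted. That gives sites a route to an answer, but the RBT-attributed branches do not require them to use it.

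Third, the meaning of a reduced dose may be clear enough. The preceding sentence ties it to Table 5.1, and 7.2.3 and 7.2.4 are built the same way. If 150 mg daily counted, those steps would lower nothing for an ordinary participant on antiretrovirals. This makes 150 mg three times weekly the likelier reading, but the wording in 3.0 and 5.1.1 keeps the other one possible.

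Fourth, the Background sentence concerns TB treatment once the inhibitor is discontinued. It does not address a week of re-challenge with the other anti-TB drugs already back. It supports the need to reconcile the rules, but does not show that the re-challenge interval is under-treated.

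**Conclusion.** The point holds as an unresolved conflict of scope in the RBT-attributed branches of 7.2.1 and 7.2.2. For at least 7 days with RBT on and LPV/r off, the same participant can fall under 450 or 1050 mg per week by one set of instructions and 2100 mg per week by another. The protocol does not say which governs. In the LPV/r-attributed branches the RBT dose is simply missing. Only Arms A and C are affected.

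This rests on two conditions: that a toxicity hold can be read as a premature stop of LPV/r, which the wording allows but does not state, and that sites find no resolving instruction in the documents, which contain none.

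A reader might also infer that the conflict distorts comparisons of TB failure, relapse or rifamycin resistance with Arm B. The documents do not support this. They give no frequency for these events, SAP 1.6 says accrual period 2 will not open, accrual period 1 was planned at 20 per arm, and the SAP plans no comparison of those TB outcomes. Whether a 7-day tolerance test without LPV/r is informative is a clinical judgement and no part of this point.

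**What to change.** Issue a clarification memo that reconciles 7.2.1 and 7.2.2 with the Schema, the note in 3.0, the notes in 5.1.1 and Table 5.1. It should:

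- state whether the rule for discontinued LPV/r applies during a temporary toxicity hold, or whether section 7.2 takes precedence;
- give a single RBT instruction for the interval when RBT is on and LPV/r is off, in both the RBT-attributed and the LPV/r-attributed branches;
- say when that instruction changes as LPV/r restarts;
- define the reduced dose, so that it is clear whether 150 mg daily counts.

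The clinical team must choose the dose; this review takes no position on it. The cost is drafting and distributing the memo, with no added visits, tests or procedures.
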